5.4.5 Rescue Medications & Supportive Care

5.4.5.1 Supportive Care Guidelines

Subjects should receive appropriate supportive care measures as deemed necessary by the treating investigator. Suggested supportive care measures for the management of adverse events with potential immunologic etiology are outlined below and in greater detail in the ECI guidance document. Where appropriate, these guidelines include the use of oral or intravenous treatment with corticosteroids as well as additional anti-inflammatory agents if symptoms do not improve with administration of corticosteroids. Note that several courses of steroid tapering may be necessary as symptoms may worsen when the steroid dose is decreased. For each disorder, attempts should be made to rule out other causes such as metastatic disease or bacterial or viral infection, which might require additional supportive care. The treatment guidelines are intended to be applied when the investigator determines the events to be related to pembrolizumab.

Note: if after the evaluation the event is determined not to be related, the investigator is instructed to follow the ECI reporting guidance but does not need to follow the treatment guidance (as outlined in the ECI guidance document). Refer to Section 6 for dose modification.

It may be necessary to perform conditional procedures such as bronchoscopy, endoscopy, or skin photography as part of evaluation of the event. Suggested conditional procedures, as appropriate, can be found in the ECI guidance document.

- **Suggestions for Pneumonitis:**
 - For **Grade 2 events**, treat with systemic corticosteroids. When symptoms improve to Grade 1 or less, steroid taper should be started and continued over no less than 4 weeks.
 - For **Grade 3-4 events**, immediately treat with intravenous steroids. Administer additional anti-inflammatory measures, as needed.
 - Add prophylactic antibiotics for opportunistic infections in the case of prolonged steroid administration.
- **Suggestions for Diarrhea/Colitis:**

Subjects should be carefully monitored for signs and symptoms of enterocolitis (such as diarrhea, abdominal pain, blood or mucus in stool, with or without fever) and of bowel perforation (such as peritoneal signs and ileus).

CONFIDENTIAL

This document is confidential. Do not disclose or use except as authorized.

- Advise all subjects who experience diarrhea/colitis to drink liberal quantities of clear fluids. If sufficient oral fluid intake is not feasible, substitute fluid and electrolytes via IV infusion. For Grade 2 or higher diarrhea, consider GI consultation and endoscopy to confirm or rule out colitis.
- For **Grade 2 diarrhea/colitis** that persists greater than 3 days, administer oral corticosteroids.
- For **Grade 3 or 4 diarrhea/colitis** that persists > 1 week, treat with intravenous steroids followed by high dose oral steroids.
- When symptoms improve to Grade 1 or less, start steroid taper and continue over no less than 4 weeks.

- **Suggestions for Type 1 diabetes mellitus (if new onset, including diabetic ketoacidosis [DKA]) or ≥ Grade 3 Hyperglycemia, if associated with ketosis (ketonuria) or metabolic acidosis (DKA)**
 - For **T1DM** or **Grade 3-4** Hyperglycemia
 - Insulin replacement therapy is recommended for Type 1 diabetes mellitus and for Grade 3-4 hyperglycemia associated with metabolic acidosis or ketonuria.
 - Evaluate patients with serum glucose and a metabolic panel, urine ketones, glycosylated hemoglobin, and C-peptide.

- **Suggestions for Hypophysitis:**
 - For **Grade 2** events, treat with corticosteroids. When symptoms improve to Grade 1 or less, start and continue steroid taper over no less than 4 weeks. Replacement of appropriate hormones may be required as the steroid dose is tapered.
 - For **Grade 3-4** events, treat with an initial dose of IV corticosteroids followed by oral corticosteroids. When symptoms improve to Grade 1 or less, start and continue steroid taper over no less than 4 weeks. Replacement of appropriate hormones may be required as the steroid dose is tapered.

- **Suggestions for Hyperthyroidism or Hypothyroidism:**

Thyroid disorders can occur at any time during treatment. Monitor patients for changes in thyroid function (at the start of

CONFIDENTIAL

This document is confidential. Do not disclose or use except as authorized.

treatment, periodically during treatment, and as indicated based on clinical evaluation) and for clinical signs and symptoms of thyroid disorders.

- **Grade 2** hyperthyroidism events (and **Grade 2-4** hypothyroidism):
 - In hyperthyroidism, non-selective beta-blockers (e.g. propranolol) are suggested as initial therapy.
 - In hypothyroidism, thyroid hormone replacement therapy, with levothyroxine or liothyronine, is indicated per standard of care.
- **Grade 3-4** hyperthyroidism
 - Treat with an initial dose of IV corticosteroid followed by oral corticosteroids. When symptoms improve to Grade 1 or less, steroid taper should be started and continued over no less than 4 weeks. Replacement of appropriate hormones may be required as the steroid dose is tapered.
- **Suggestions for Hepatic Events:**
 - For **Grade 2** events, monitor liver function tests more frequently until returned to baseline values (consider weekly).
 - Treat with IV or oral corticosteroids
 - For **Grade 3-4** events, treat with intravenous corticosteroids for 24 to 48 hours.
 - When symptoms improve to Grade 1 or less, a steroid taper should be started and continued over no less than 4 weeks.
- **Suggestions for Renal Failure or Nephritis:**
 - For **Grade 2** events, treat with corticosteroids.
 - For **Grade 3-4** events, treat with systemic corticosteroids.
 - When symptoms improve to Grade 1 or less, steroid taper should be started and continued over no less than 4 weeks.
- **Suggestions for Management of Infusion Reactions:** Signs and symptoms usually develop during or shortly after drug infusion and generally resolve completely within 24 hours of completion of infusion.

Table 5.4 below shows treatment suggestions for subjects who experience an infusion reaction associated with administration of pembrolizumab (MK-3475).

Table 5.4 Infusion Reaction Treatment Suggestions

CONFIDENTIAL

This document is confidential. Do not disclose or use except as authorized.

NCI CTCAE Grade	Treatment	Premedication at subsequent dosing
Grade 1 Mild reaction; infusion interruption not indicated; intervention not indicated	Increase monitoring of vital signs as medically indicated until the subject is deemed medically stable in the opinion of the investigator.	None
Grade 2 Requires infusion interruption but responds promptly to symptomatic treatment (e.g., antihistamines, NSAIDs, narcotics, IV fluids); prophylactic medications indicated for < =24 hrs	Stop infusion and monitor symptoms. Additional appropriate medical therapy may include but is not limited to: IV fluids Antihistamines NSAIDs Acetaminophen Narcotics Increase monitoring of vital signs as medically indicated until the subject is deemed medically stable in the opinion of the investigator. If symptoms resolve within one hour of stopping drug infusion, the infusion may be restarted at 50% of the original infusion rate (e.g., from 100 mL/hr to 50 mL/hr). Otherwise dosing will be held until symptoms resolve and the subject should be premedicated for the next scheduled dose. Subjects who develop Grade 2 toxicity despite adequate premedication should be permanently discontinued from further trial treatment administration.	Subject may be premedicated 1.5h (± 30 minutes) prior to infusion of pembrolizumab (MK-3475) with: Diphenhydramine 50 mg po (or equivalent dose of antihistamine). Acetaminophen 500-1000 mg po (or equivalent dose of antipyretic).
Grades 3 or 4 Grade 3: Prolonged (i.e., not rapidly responsive to symptomatic medication and/or brief interruption of infusion); recurrence of symptoms following initial improvement; hospitalization indicated for other clinical sequelae (e.g., renal impairment, pulmonary infiltrates) Grade 4: Life-threatening; pressor or ventilatory support indicated	Stop Infusion. Additional appropriate medical therapy may include but is not limited to: IV fluids Antihistamines NSAIDs Acetaminophen Narcotics Oxygen Pressors Corticosteroids Epinephrine Increase monitoring of vital signs as medically indicated until the subject is deemed medically stable in the opinion of the investigator. Hospitalization may be indicated. Subject is permanently discontinued from further trial treatment administration.	No subsequent dosing
Appropriate resuscitation equipment should be available in the room and a physician readily available during the period of drug administration.		

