5.4.2 Prohibited Concomitant Medications

Subjects are prohibited from receiving the following therapies during the Screening and Treatment Phase (including retreatment for post-complete response relapse) of this trial:

- Antineoplastic systemic chemotherapy or biological therapy
- Immunotherapy not specified in this protocol
- Chemotherapy not specified in this protocol
- Investigational agents other than pembrolizumab not specified in this protocol

CONFIDENTIAL

This document is confidential. Do not disclose or use except as authorized.

- Live vaccines within 30 days prior to the first dose of trial treatment and while participating in the trial. Examples of live vaccines include, but are not limited to, the following: measles, mumps, rubella, varicella/zoster, yellow fever, rabies, BCG, and typhoid vaccine.
- Systemic glucocorticoids for any purpose other than to modulate symptoms from an event of clinical interest of suspected immunologic etiology. The use of physiologic doses of corticosteroids may be approved after consultation with the Overall PI.
- Strong inhibitors/inducers of selected CYP450 isoenzymes. Dabrafenib mesylate is a substrate for CYP 3A4, 2C8, p-glycoprotein (Pgp), and breast carcinoma resistance protein (Bcrp). These enzymes and transporters are prohibited for eligibility and during the study. Because the lists of these agents are constantly changing, it is important to regularly consult a frequently-updated list such as <http://medicine.iupui.edu/clinpharm/ddis/table.aspx>; medical reference texts such as the Physicians' Desk Reference may also provide this information.
- Concomitant medications should be reviewed for the potential risk of inducing nephrotoxicity and, if so, should be modified if clinically possible (See 6.2.6)

If there is a clinical indication for one of these or other medications or vaccinations specifically prohibited during the trial, discontinuation from trial therapy or vaccination may be required. The investigator should discuss any questions regarding this with the Merck Clinical team. The final decision on any supportive therapy or vaccination rests with the subject's primary investigator. Subjects may receive other medications that the investigator deems to be medically necessary.

The Exclusion Criteria describes other medications that are prohibited in this trial.

There are no prohibited therapies during the Post-Treatment Follow-up Phase.

CONFIDENTIAL

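### Section 5.4.5.1 sets a later steroid trigger for Grade 3-4 diarrhea/colitis (more than 1 week) than for Grade 2 (more than 3 days)

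*Combined protocol and SAP*

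**What the plan says.** The diarrhea/colitis suggestions in Section 5.4.5.1 contain two adjacent steroid bullets.

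- Grade 2 diarrhea/colitis "that persists greater than 3 days, administer oral corticosteroids".
- Grade 3 or 4 diarrhea/colitis "that persists > 1 week, treat with intravenous steroids followed by high dose oral steroids".

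The section limits its own reach: "The treatment guidelines are intended to be applied when the investigator determines the events to be related to pembrolizumab". It also leaves room for judgement: "Subjects should receive appropriate supportive care measures as deemed necessary by the treating investigator". It refers to an ECI guidance document for more detail; that document is not in the file.

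For Grade 2 and above, the same list asks sites to "consider GI consultation and endoscopy to confirm or rule out colitis", with no waiting period. Severe events in other organs are handled without a wait: Grade 3-4 pneumonitis, "immediately treat with intravenous steroids. Administer additional anti-inflammatory measures, as needed"; Grade 3-4 hepatic events, "treat with intravenous corticosteroids for 24 to 48 hours".

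**The concern.** A duration threshold for starting steroids should not lengthen as the event becomes more severe. Here it does. A site that follows the two bullets literally would start oral steroids on day 4 of a persistent Grade 2 event, but would find no systemic steroid suggestion for a Grade 3 or 4 event until it had passed one week. The same section asks sites to watch these patients for bowel perforation, and Table 6.1 permanently stops pembrolizumab for Grade 4, so the protocol itself treats severe colitis as dangerous.

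What is at stake is the clarity of safety guidance for severe events with a rapid onset. The efficacy design is not involved.

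**Working it through.** **Step 1: the two triggers as days.**

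| Grade | Condition in Section 5.4.5.1 | First day the steroid suggestion applies |
|---|---|---|
| 2 | more than 3 days | day 4 |
| 3 or 4 | more than 1 week (7 days) | day 8 |

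Difference: 7 − 3 = 4 days, that is, days 4, 5, 6 and 7.

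**Step 2: when the 4-day window holds.** The section does not say whether the clock runs from the onset of diarrhea or from the onset of the current grade.

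- If the event is Grade 3-4 from day 1, both clocks agree and the window is days 4 to 7.
- If it is Grade 2 on days 1 and 2 and becomes Grade 3 on day 3, a clock from diarrhea onset gives the same window. A clock from grade onset gives a first steroid day of 3 + 7 = 10, so the window is days 4 to 9.
- If it was Grade 2 for more than 3 days before worsening, the Grade 2 bullet had already applied.

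The gap therefore concerns events that reach Grade 3-4 within the first 3 days. The figure of days 4 to 7 is exact for those that are Grade 3-4 from day 1.

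**Step 3: does any other text fill the gap?**

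- The Grade 2 steroid bullet names Grade 2 alone. The neighboring work-up sentence is expressly for Grade 2 and above, so the wider wording was used where it was meant.
- Table 6.1 (Section 6.1) covers holding, restarting and stopping pembrolizumab. It mentions reducing steroids but not when to start them.
- Table 6-9 (Section 6.2.10) is written for dabrafenib and trametinib. For Grade 3-4 it allows second-line therapies if indicated, with no one-week wait. Its Grade 1-2 row names budesonide among such therapies. It gives no systemic steroid trigger.
- Section 5.4.2 governs which steroid use is permitted, not when to start it.

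None of these gives an earlier systemic steroid trigger for Grade 3-4.

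**Step 4: comparison across organs.** Six disorders in the list have a Grade 3-4 steroid instruction: pneumonitis, diarrhea/colitis, hypophysitis, hyperthyroidism, hepatic events and renal events. Only diarrhea/colitis has a waiting period.

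**Step 5: illustrative frequency.** Section 2.2.1.5 gives immune-mediated colitis in 1% of 411 melanoma patients on pembrolizumab, grade unstated. Treat every such case as Grade 3-4 lasting to day 4 (an assumption). Expected cases = n × p; chance of at least one = 1 − (1 − p)^n.

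| n | Basis | p | Expected cases | Chance of at least one |
|---|---|---|---|---|
| 14 | one first stage | 0.01 | 0.14 | 1 − 0.99^14 = 0.13 |
| 25 | one full cohort | 0.01 | 0.25 | 1 − 0.99^25 = 0.22 |
| 50 | both cohorts full (Section 13.2) | 0.01 | 0.50 | 1 − 0.99^50 = 0.39 |
| 50 | 1% rounded up from 0.5% | 0.005 | 0.25 | 1 − 0.995^50 = 0.22 |
| 50 | 1% rounded down from 1.5% | 0.015 | 0.75 | 1 − 0.985^50 = 0.53 |

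These figures are not bounds. The bullet covers diarrhea as well as colitis, and Section 2.2.1.5 lists diarrhea among reactions in at least 20% of patients. The documents give no Grade 3-4 share and no colitis rate for the three drugs together.

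**The case against.** The strongest defense is that the text only suggests. Supportive care is left to the treating investigator, and more detail is said to sit in the ECI guidance document. If that document starts steroids earlier for Grade 3-4, sites may lack nothing in practice. This stands as a limit on the consequence: the defect is shown for the protocol text only. It does not remove the inversion. If the other document starts earlier, the two disagree; if it repeats the week, the inversion is in both.

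A reader might infer that the protocol withholds or forbids steroids for severe colitis during the first week. The documents do not support that. Section 5.4.2 prohibits "Systemic glucocorticoids for any purpose other than to modulate symptoms from an event of clinical interest of suspected immunologic etiology", and that exception leaves earlier use open for a suspected immunologic event. Silence on days 4 to 7 is not an instruction to withhold.

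A reader might also infer that all management of severe colitis is delayed. It is not. Table 6.1 holds pembrolizumab for Grade 2-3 and stops it for Grade 4 without a one-week wait. Fluids and the suggested GI work-up are not delayed either. During targeted therapy, Table 6-9 makes clinical evaluation mandatory for Grade 3-4 and interrupts those drugs.

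The cross-organ comparison is also open to challenge. Diarrhea/colitis is the only disorder in the list with a steroid wait at either grade, so being the only Grade 3-4 entry with one does not prove an error. That is fair. The finding rests on the comparison of Grade 2 with Grade 3-4 inside the same list.

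**Conclusion.** The inversion is real and in the current text: for pembrolizumab-related diarrhea/colitis, the worse grade has the later steroid trigger. The gap is 4 days (days 4 to 7) for an event that is Grade 3-4 from day 1. For other events it depends on an unstated clock. Confidence is high in the textual inconsistency and lower in its practical consequence, because the text is advisory, earlier steroids are allowed, and the ECI guidance document could not be checked.

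How many patients would be affected is unknown. The 0.5 expected cases in 50 patients assumes that both cohorts fill, that the 1% rate applies to this three-drug or two-drug setting, and that every colitis case is severe. It should not be quoted as an upper limit.

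No endpoint, sample size, decision rule or analysis is affected. This should be fixed because it is wrong as written, concerns a potentially serious event, and costs almost nothing to correct.

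**What to change.** In the Grade 3-4 diarrhea/colitis bullet of Section 5.4.5.1, make one of two edits:

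- delete the one-week persistence condition, so that the steroid suggestion applies to Grade 3 or 4 without a wait; or
- replace it with a trigger no later than the Grade 2 trigger, that is, more than 3 days at the latest.

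Either edit removes the inconsistency. The choice between them is clinical. The medical lead should set the exact timing, align it with the ECI guidance document, and state when the clock starts if any duration condition is kept. The rule that the guidance applies to events the investigator judges related to pembrolizumab stays as it is.

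Cost: one line of protocol wording and a notice to sites. Design, sample size and analysis are unchanged.

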5.5 Criteria for Taking a Participant off Protocol Therapy

Duration of therapy will depend on individual response, evidence of disease progression and tolerance. In the absence of treatment delays due to adverse events, treatment may continue until one of the following criteria applies:

- Completion of two years of pembrolizumab therapy
- Disease progression, unless patient meets criteria for treatment beyond progression in Section 5.5.1
- Intercurrent illness that prevents further administration of treatment,

CONFIDENTIAL

This document is confidential. Do not disclose or use except as authorized.

- Unacceptable adverse event(s),
- Participant demonstrates an inability or unwillingness to comply with the oral medication regimen and/or documentation requirements
- Participant decides to withdraw from the study, or
- General or specific changes in the participant's condition render the participant unacceptable for further treatment in the opinion of the treating investigator.

5.5.1 Treatment Beyond Progression

Following initial disease progression, if a participant is treated beyond progression per the criteria outlined below, tumor assessments must be repeated ≥ 4 weeks after initial disease progression in order to confirm disease progression. The tumor assessment must not be repeated any sooner than 4 weeks after initial disease progression.

Treatment beyond progression will be allowed. In general, patients who develop disease progression (per RECIST1.1) will remain on trial. Since this trial potentially involves four specific treatments “zones”, namely 1) MTT induction; 2) concomitant MTT plus pembrolizumab; 3) pembrolizumab single-agent; and 4) follow up after pembrolizumab discontinuation in setting of CR, the specific treatment beyond progression will be dependent on which “zone” the patient is in when progression occurs as described below.

5.5.1.1 MTT Induction (Targeted Therapy Lead-In)

Patients who develop clinical progression or radiographic progression (e.g. if non-planned imaging is performed) during MTT induction, then patients will be allowed to move onto the concomitant MTT plus pembrolizumab phase of the therapy.

5.5.1.2 Concomitant MTT plus pembrolizumab (Combined Targeted Therapy Plus)

Patients who develop clinical progression during or radiographic during (e.g. if non-planned imaging is performed) or on routine imaging performed at the end of the concomitant MTT plus pembrolizumab phase will be allowed to be treated with single-agent pembrolizumab beyond progression as long as the following criteria are met:

- A. Absence of signs and symptoms (including worsening of laboratory values) indicating disease progression.
- B. No decline in ECOG performance status.
- C. Absence of rapid progression of disease.
- D. Absence of progressive tumor at critical anatomical sites (e.g., cord compression) requiring urgent alternative medical intervention.

CONFIDENTIAL

This document is confidential. Do not disclose or use except as authorized.

5.5.1.3 Pembrolizumab single-agent

Patients who develop progression of disease on the pembrolizumab single-agent phase will be allowed to be treated beyond progression as long as the following criteria are met:

- A. Absence of signs and symptoms (including worsening of laboratory values) indicating disease progression.
- B. No decline in ECOG performance status.
- C. Absence of rapid progression of disease.
- D. Absence of progressive tumor at critical anatomical sites (e.g., cord compression) requiring urgent alternative medical intervention.

